### 6.3.2 Disallowed Therapy

A disallowed medication may be administered in an emergency if the subject's safety is in jeopardy. If possible, the Medical Monitor should be consulted prior to administration of the disallowed medication (if not feasible, then as soon as possible afterwards) to determine whether the subject may continue in the study.

If a subject has taken any disallowed medication for any reason other than rescue therapy, record this as a protocol deviation and immediately contact Bausch + Lomb.

Disallowed medications include, but are not limited to the following:

**Table 2: Disallowed Therapies**

Medication/Class of Drug	Status
Acetylsalicylic Acid > 81mg/day	Excluded starting 2 days before surgery and through 18 days after surgery
Antihistamines (H-1 Antagonist), systemic or ocular	Excluded starting 2 days before surgery and through 18 days after surgery
Artificial Tears	Excluded starting 7 days before surgery and through 18 days after surgery
Biologic Agents (example: anti-TNF- $\alpha$ [eg, Cimzia])	Excluded starting the day of surgery and through 18 days after surgery
Corticosteroids/Glucocorticoids: systemic, inhaled, or ocular	Excluded starting 14 days before surgery and through 18 days after surgery
Decongestants, systemic or ocular	Excluded starting 2 days before surgery and through 18 days after surgery
Flomax (tamsulosin)	Excluded starting 7 days before surgery and through 18 days after surgery
Hydrocodone/Opioid-Based Pain Medications	Excluded starting the day of surgery and through 18 days after surgery (can be used ONLY during surgery)
Ocular Hypotensive Medication, oral (eg, Diamox)	Excluded except for use during IOP one-time intervention at V3
Ocular Hypotensive Medication, topical (eg, Betaxolol)	Excluded except for use during IOP one-time intervention at V3
Immunosuppressants, systemic or ocular	Excluded starting 30 days before surgery and through 18 days after surgery
Mast cell Stabilizers, systemic or ocular	Excluded starting 2 days before surgery and through 18 days after surgery
Methotrexate/DMARDs	Excluded starting 30 days before surgery and through 18 days after surgery
NSAIDs and COX-2 Inhibitors, systemic or ocular	Excluded starting 2 days before surgery and through 18 days after surgery
Plaquinil/Anti-malarial drugs	Excluded starting 30 days before surgery and through 18 days after surgery
Propoxyphene	Excluded starting 2 days before surgery and through 18 days after surgery
Serratiopeptidase	Excluded starting 7 days before surgery and through 18 days after surgery

Abbreviations: COX, cyclooxygenase; DMARD, disease-modifying anti-rheumatic drugs; TNF, tumor necrosis factor.

**Additionally, any medication the subject uses that the Investigator and/or Medical Monitor feels may interfere with subject safety or study parameters should be considered a disallowed medication.**

Disallowed medication that is used for persistent or worsening inflammation is called “Rescue Medication” and is discussed in [Section 6.2.3.1](#). Subjects taking rescue medication must stop

using the study drug and be withdrawn from study participation. Subjects requiring rescue medication will be considered treatment failures.

#### **6.4 Treatment Compliance**

Any subject who does not follow instructions to a degree that, in the opinion of the Sponsor or the Investigator, jeopardizes the subject's well-being or the validity of the study, must be discontinued.

Subjects will be given study drug administration diaries to record the date and time of each study medication instillation. Treatment compliance during the study will be documented by subject entries in the study diaries. Study personnel will instruct the subject to bring the study diary to each of their follow-up visit(s) and remind subjects that no information other than dosing information should be recorded in the diary.

#### **6.5 Protocol Deviations**

Protocol deviations will be defined prior to first subject first visit (see [Section 8.5.6](#)). The IRB/EC definitions for protocol deviations will be assumed by inference to be part of this protocol, if available. The definition of protocol deviation severity may change during the study and all major protocol deviations will be identified prior to database lock.

The date and reason for any protocol deviation will be documented in all cases. Significant or major protocol deviations impacting the safety of the subject or the integrity of the study must be reported by the Investigator to the IRB/EC and the Sponsor immediately. Reporting of all other protocol deviations must adhere to the requirements of the governing IRB/EC.

Protocol deviation assessments will continue for all subjects until the end of the study, unless the protocol deviations put a subject at risk or the subject's condition requires that he/she be discontinued from the study.

### **7.0 ADVERSE EVENTS**

#### **7.1 Definition of Adverse Events**

- Any untoward medical occurrence (including an abnormal laboratory finding) in a subject participating in a clinical study that does not necessarily have a causal relationship with the study protocol and/or procedure or with the study treatment.
- Any unfavorable and unintended sign (including an abnormal laboratory finding), symptom, or disease with onset following the signing of informed consent through study exit, whether or not considered related to the study. An AE can also include a progression/worsening of underlying disease, hypersensitivity, and extravasation.
- Events occurring from drug overdose, whether accidental or intentional, events occurring from drug abuse, drug misuse, drug interactions, drug dependency, events occurring from drug withdrawal, and medication errors.

- A treatment-emergent AE (TEAE) is defined as an AE with a start date on or after the first dose of study drug, or that worsened following first administration of study drug.

## 7.2 Definition of Serious Adverse Events

Information about every serious adverse event (SAE) will be collected and recorded. An SAE is any adverse drug experience occurring at any dose that results in any of the following outcomes:

- Death
- A life-threatening adverse drug experience
- Inpatient hospitalization or prolongation of existing hospitalization
- A persistent or significant disability/incapacity
- A congenital anomaly/birth defect
- Is sight-threatening (may result in persistent or significant loss of vision)
- Encompasses any medically significant event that may jeopardize a subject and may require medical or surgical intervention to prevent any of the outcomes listed above
- Is medically significant, as determined by the Principal Investigator or medically qualified Sub-Investigator

A medically significant event that does not result in any of the above may be considered an SAE when, based upon appropriate medical judgment, the event may jeopardize a subject and may require medical or surgical intervention to prevent one of the outcomes listed in this definition.

Important medical events that may not have resulted in death, be life-threatening, or require hospitalization may be considered an SAE when, based upon appropriate medical judgment, they may jeopardize the subject and may require medical or surgical intervention to prevent one of the outcomes listed in this definition. Examples of such medical events include allergic bronchospasm requiring intensive treatment in an emergency room or at home, blood dyscrasias or convulsions that do not result in inpatient hospitalization, or the development of drug dependency or drug abuse.

Additionally, any suspected transmission of an infectious agent by a Bausch + Lomb product, pathogenic or non-pathogenic, is considered an SAE. The event may be suspected from clinical symptoms or laboratory findings indicating an infection in a subject exposed to a Bausch + Lomb product. The terms “suspected transmission” and “transmission” are considered synonymous.

Hospitalization is a criterion for assessment of seriousness. To qualify as serious under the criteria of “hospitalization,” a hospital admission of at least a 24-hour period is required. If a

subject is retained the emergency room greater than 24 hours, but not admitted for medical care, these cases should be evaluated individually, as criteria such as “medically significant” may also apply.

Hospitalization without a medical AE should not be considered either serious, or an AE. Examples include:

- Admission for treatment of a pre-existing condition not associated with the development of a new AE or with worsening of the pre-existing condition (eg, for work-up of persistent pre-treatment lab abnormality).
- Hospitalization for a purpose unrelated to the study (eg, “planned” or elective surgery scheduled prior to study participation) would not ordinarily need to be reported, unless a complication occurred which otherwise caused prolongation of this hospitalization.
- Protocol-specified admission or procedure (eg, cataract surgery required by a study protocol; or overnight stay for monitoring due to protocol required surgery, *with no associated SAE or complication necessitating prolonged stay*)
- Social admission (eg, social hospitalization for purposes of respite care)

### 7.3 Reporting Adverse Events and Follow-up

Throughout the course of the study, efforts will be made by the Investigator to remain alert to possible AEs that are either systemic or ocular in nature. The period of observation for collection of AEs extends from the time the subject gives informed consent until the last study visit or discontinuation from the study. The first concern will be the safety of the subject, and appropriate medical intervention will be made.

The Investigator or designee will elicit reports (ie, via direct questioning, observation, clinical evaluation) of AEs from the subject at each study visit and record all AEs. The Investigator will document the dates of onset, progress, outcome, and resolution of such AEs. The Investigator will also provide an assessment of all AEs as to the severity, causal relationship to study drug, and causal relationship to study protocol.

#### 7.3.1 Causality

The terms used to assess the causal relationship of the event to the study drug are:

- **Related:** There is at least a reasonable possibility that the AE/SAE is related to the study drug. Reasonable possibility means that there is evidence to suggest a causal relationship between the drug and the AE.
- **Not Related:** There is little or no reasonable possibility that the AE/SAE is related to the study drug. This assessment implies that the AE/SAE has little or no temporal relationship to the study drug and/or a more likely or certain alternative etiology exists.

When the investigator assesses the AE as “not related”, an alternative etiology (ie, concomitant drug, medical history, prior AE, or other etiologic reasons) must be provided.

The subject will be instructed to contact the Investigator immediately if he/she notices any unusual systemic or ocular AEs between visits.

Additional assessments/visits may be scheduled, as necessary, to ensure the safety of the subject, during the study period.

### 7.3.2 Severity

The term “severe” is often used to describe the intensity (severity) of a specific event (as in mild, moderate, or severe myocardial infarction); the event itself however may be of relatively minor medical significance (such as severe headache).

The terms used to assess the severity of the event are:

- **Mild:** Awareness of signs or symptoms, but easily tolerated and are of minor irritant type causing no loss of time from normal activities. Symptoms do not require therapy or a medical evaluation; signs and symptoms are transient.
- **Moderate:** Events introduce a low level of inconvenience or concern to the subject and may interfere with daily activities, but are usually improved by simple therapeutic measures; moderate experiences may cause some interference with functioning.
- **Severe:** Events interrupt the subject’s normal daily activities and generally require systemic drug therapy or other treatment; they are usually incapacitating.

### 7.3.3 Follow-Up

A subject who discontinues due to an AE should be seen for post-study follow-up visits as necessary.

When the severity and nature of the non-serious AEs (including non-related AEs of special interest, such as IOP increase, and non-serious AEs that are deemed not related to the study drug) that are ongoing at the study exit visit warrants a follow-up, the Investigator will do so as in the case of SAEs.

## 7.4 Reporting Serious Adverse Events and Follow-up

Any SAE must be reported to SynteractHCR Safety, independent of the circumstance or suspected cause, within 24 hours from the time the event was reported to the Investigator. All SAEs experienced from the date of consent through at least 30 days after the last dose of study drug must be reported to Synteract HCR regardless of the relationship to the study drug or the protocol. For events occurring beyond the minimum 30-day period after the last dose of study drug, or for any timeframe afterward deemed medically significant, only SAEs considered related to the study drug should be reported promptly to Synteract HCR Safety.

Within 24 hours of notification the Investigator will fax a completed Serious Adverse Event Report to the SynteractHCR contact noted on the [Personnel and Facilities](#) page. For SAEs with fatal outcomes, a summary of available autopsy findings should be submitted as soon as possible.

The Investigator will notify their IRB in writing of any SAE in accordance with the IRB requirements. For sites using a Central IRB (CIRB), Synteract HCR Clinical will notify the CIRB on their behalf.

Bausch + Lomb or its designee will be responsible for submitting SAE reports to regulatory authorities based on applicable regulations. Synteract HCR will be responsible to a notification to all participating Investigators of any SAE that is unexpected and associated with the study (refer to Section 7.6). If the Investigator becomes aware of any new information regarding an SAE (ie, resolution, change in condition, or new treatment), a new SAE Form must be completed and faxed to SynteractHCR Safety within 24 hours. The original SAE form is not to be altered. The report should be marked as a “follow-up report” and describe whether the event has resolved or continues and how the event was treated.

Serious adverse events that have previously been reported and that continue after the subject's discontinuation or completion of the study will be followed until their medical endpoints are determined or until no further change in the conditions is expected. The events and endpoints will be reported in writing by the Investigator to SynteractHCR Safety. Following the subject's discontinuation or completion of the study, for any timeframe afterward deemed medically significant, any SAEs that are assessed as causally related to study drug should also be reported to SynteractHCR Safety.

## **7.5 Reporting Pregnancies and Follow-up**

In the event that a study subject or a study subject's partner becomes pregnant during the course of the study or within 7 calendar days after last dose of study drug, the study site will complete the Pregnancy Reporting form and will forward the completed form to the study Medical Monitor and the SynteractHCR Safety contact noted in the [Personnel and Facilities](#) page within 24 hours of the time the pregnancy was reported to the Investigator. The study site should also notify the IRB of the pregnancy, in accordance with IRB requirements. All pregnancies will be followed to term (in the event that a study subject's partner becomes pregnant, permission to follow the pregnancy needs to be granted by the partner). Every effort will be made to obtain the health status of the mother and infant or the fetus (including cases of miscarriage or therapeutic abortion). Pregnancy outcome information must be documented on a follow-up Pregnancy Reporting form and submitted to the Medical Monitor, Synteract HCR and IRB.

The subject will be discontinued from the study to stop exposure of the study drug to the fetus.

## **7.6 Submitting an Expedited Safety Report to the IRB (Central or Local)**

Any suspected, unexpected, serious adverse reaction (SUSAR) warrants expedited reporting. In addition, any unexpected SAE related to a subject's participation in the study (or conduct of study), regardless if the study drug was administered, will be evaluated by Bausch + Lomb Global Safety and Vigilance to determine if expedited reporting is required. For example, an unexpected, serious and severe reaction which could be associated to the study procedures, and which could modify the study conduct requires expedited reporting.

Each expedited safety report will routinely include a brief cover memorandum, the completed MedWatch Form FDA 3500A or Council for International Organizations of Medical Sciences I

Form, a clinical analysis of the event with any similar events that have occurred with the product, and any additional pertinent information recommended by the study Medical Monitor. Once the report is compiled by Global Safety and Vigilance, the site Investigator must submit the expedited safety report to the local IRB/EC within the required reporting timeframe. Follow-up reports should be submitted when requested or when pertinent information becomes available. The site principal Investigator must retain a complete copy of each expedited safety report as it was submitted to the IRB. It is important that the principal Investigator review these expedited reports, as they contain safety information that may be relevant to each of the participating subjects.

## **8.0 STATISTICAL METHODS**

### **8.1 Study Endpoints**

#### **8.1.1 Primary Efficacy Endpoints**

The primary efficacy endpoints for this study are:

1. The proportion of subjects with complete resolution of anterior chamber (AC) cells (cell score = 0) in the study eye at Visit 5 (Postoperative Day 8) for LE gel 0.38% and vehicle
2. The proportion of subjects with Grade 0 pain in the study eye at Visit 5 (Postoperative Day 8) for LE gel 0.38% and vehicle

#### **8.1.2 Secondary Efficacy Endpoints**

The secondary efficacy endpoints for this study include:

- Proportion of subjects with complete resolution of AC cells in the study eye at each visit and for each subject's final on-treatment visit
- Proportion of subjects with Grade 0 pain in the study eye at each visit and for each subject's final on-treatment visit
- Proportion of subjects with complete resolution of AC flare in the study eye at each visit and for each subject's final on-treatment visit
- Proportion of subjects with complete resolution of AC cells and flare in the study eye at each visit and for each subject's final on-treatment visit
- Change from baseline in AC cells and flare, combined and separately, at each follow-up visit
- Proportion of treatment failures at Visit 5 (Postoperative Day 8)

Other secondary or exploratory efficacy analyses may also be carried out as described in the study Statistical Analysis Plan.

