Statistical Methods:	
Sample Size
 
Approximately 588 subjects will be randomized in a 2:2:1:1 ratio to LE gel 0.38% TID, LE gel 0.38% BID, vehicle TID, and vehicle BID.
 
The 2 vehicle arms will be combined into 1 treatment group in the statistical analysis, and hence the study will have 3 treatment groups, ie, LE gel 0.38% TID, LE gel 0.38% BID, and (combined) vehicle groups. Each of the three treatment groups will consist of approximately 196 subjects.
 
Regarding complete resolution of AC cells, a sample size of 196 subjects will provide 87% power to detect each of the two expected differences (BID and TID dosing). The two simultaneous tests will have 95% power to detect at least one of the two differences and 80% power to detect both differences.
 
Under the planned gatekeeping hypothesis testing strategy, the power of each pain resolution hypothesis is limited by the power of the corresponding AC cells resolution hypothesis. In the event that the corresponding AC cells hypothesis is rejected, each pain hypothesis test has 99% power to detect the expected difference.
 
Estimates of efficacy used to calculate the sample size were based on the integrated database of 4 previous similar studies. Two of these studies were conducted with LE gel 0.5% QID and vehicle. One study was conducted with LE gel, 0.38%, dosed TID and BID. One study was conducted with LE gel, 0.38%, dosed BID.
 
Primary Endpoints
 
The primary efficacy endpoints for this study are:
 
 
1. The proportion of subjects with complete resolution of anterior chamber (AC) cells at Visit 5 (Postoperative Day 8).
 
2. The proportion of subjects with Grade 0 pain at Visit 5 (Postoperative Day 8).
 
 
Secondary Endpoints
 
The secondary endpoints for this study are:
 
 
• Proportion of study eyes with complete resolution of AC cells at each visit and for each subject's final on-treatment visit.
 
• Proportion of study eyes with Grade 0 pain at each visit and for each subject's final on-treatment visit.
 
• Proportion of study eyes with complete resolution of AC flare at each visit
 

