### Bausch & Lomb Incorporated Study #875

and for each subject's final on-treatment visit.

- Proportion of study eyes with complete resolution of AC cells and flare at each visit and for each subject's final on treatment visit.
- Change from baseline in AC cells and flare, combined and separately, at each follow-up visit.

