#### 6.2.3.1     Rescue Medication

Subjects will be assessed at Visits 4 through 7 (Postoperative Days 3, 8, 15, and 18) for treatment rescue. Subjects with worsening or no change in the grade of inflammation in the study eye compared with the previous visit are eligible and may be considered for rescue medication. For subjects who meet either of these criteria, it is at the discretion of the Investigator when to begin rescue medication. The choice of rescue medication and dosing shall also be determined by the Investigator. Subjects requiring rescue medication for inflammation will stop treatment with the study drug and will be promptly discontinued from the study. The inflammation will not be reported as an adverse event (AE). The rescue medication will be recorded on the Concomitant Medication electronic case report form (eCRF) and the exit reason will be entered as “rescue medication” in the eCRF. Subjects who receive rescue medication will be counted as treatment failures as of the date of receiving rescue medication. Subjects who require rescue medication should return within 7 days following the date that rescue medication begins in order to undergo the procedures for the early termination visit.

NOTE: Rescue med that is required at V7 will not be recorded on the ConMed eCRF

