**Table 1: Permitted Therapies**

Medication/Class of Drug	Status
Acetaminophen	Permitted
Acetylsalicylic Acid $\leq$ 81 mg/day	Permitted
Anesthetic Agents a	Permitted for surgery, IOP, and fundus examination ONLY
Antibiotic, Intracameral Injection at end of surgery b	Permitted
Antibiotic, Topical (NOT combined with a steroid) c	Permitted
Anti-Cholesterol Medications	Permitted
Antidepressants	Permitted
Antihypertensive Agents	Permitted
Antimicrobials, Systemic	Permitted
Birth Control Pills	Permitted
Cardiovascular Agents	Permitted
Epinephrine/Noradrenaline	Permitted for surgery ONLY
Estrogen Therapy	Permitted
Oral Histamine H 2 Receptor Antagonist (example: Zantac)	Permitted
Hypoglycemic Agents	Permitted
Hypotensive Medication, topical ocular	Permitted for one-time use at Day 1 post-op (Visit 3)
Insulin	Permitted
Mydriatic Agents a	Permitted for surgery and fundus examination ONLY
Neosynephrine/Phenylephrine	Permitted for surgery and fundus examination ONLY
Thyroid Preparations	Permitted

a Standard anesthetic and mydriatic agents may be used intraoperatively and for IOP and fundus examination ONLY.

b Intracameral injection of antibiotic is allowed at the end of surgery.

c Use of topical antibiotics is allowed if they are not used in combination with any steroid (eg, Zylet® or TobraDex should not be used).

**NOTE: Intraoperative use of topical antibiotics or other standard of care surgical medications should be recorded in the source documentation only. Topical antibiotics used preoperatively or postoperatively should be recorded in the Concomitant Medications eCRF provided by the Sponsor.**

Subjects requiring post-surgical treatment rescue will be considered treatment failures and subjects will stop use of study drug. Document all rescue medication use in the eCRFs.

Please refer to [Section 6.2.3.1](#) Rescue Medication on page 41 for Early Term Visit

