### Analysis of Secondary Efficacy Endpoints

Analyses of secondary efficacy endpoints will be based on the ITT population. Missing data from subjects who are rescued or have discontinued the study prior to a study visit will be handled by either of two approaches: 1) missing data are imputed as failures; or 2) the last observation prior to the rescue medication or subject discontinuation is carried forward to subsequent visits (LOCF).

With the exception of change from baseline to each follow-up visit, each of the secondary efficacy endpoints will be independently tested at each visit using similar statistical methods employed for primary efficacy endpoints (without the p-value adjustments).

Change from baseline (Visit 3) in AC cells and flare composite score (Anterior Chamber Reaction), as well as individual cells and flare scores, will be analyzed using both continuous and discrete statistical methods by treatment and visit, with missing data imputed by LOCF.

Analysis of complete resolution of AC cells and Grade 0 pain at each visit will be conducted using a Pearson Chi-squared test, with missing data imputed as failures, and also with missing data imputed by LOCF. Similar analyses will be performed for complete resolution of AC cells and flare combined and for flare separately.

Other secondary or exploratory efficacy analyses may also be carried out as described in the study Statistical Analysis Plan.

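### Does the secondary endpoint on treatment failures at Visit 5 need a new definition before it can be analysed?

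*Combined protocol and SAP*

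**What the plan says.** Secondary efficacy endpoints are listed three times. The synopsis section on study endpoints and Section 8.1.2 both include "Proportion of treatment failures at Visit 5 (Postoperative Day 8"). The synopsis Statistical Methods opens its own list with "The secondary endpoints for this study are", gives five items, and ends with "Change from baseline in AC cells and flare, combined and separately, at each follow-up visit". Treatment failures are not among them.

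The term is used in several places:

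- Section 6.2.3.1 (Rescue Medication): "Subjects who receive rescue medication will be counted as treatment failures as of the date of receiving rescue medication".
- Section 6.3.1 (Permitted Therapy): "Subjects requiring post-surgical treatment rescue will be considered treatment failures and subjects will stop use of study drug".
- Section 6.3.2 (Disallowed Therapy): "Subjects requiring rescue medication will be considered treatment failures".
- Section 8.5.9 (Missing Data) applies the same label to missing data and to stopping study or treatment before Visit 5 for whatever reason. Its opening words confine it to the primary efficacy endpoints in the ITT population.

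For the analysis, Section 8.5.1.1 says that, apart from change from baseline, "each of the secondary efficacy endpoints will be independently tested at each visit using similar statistical methods employed for primary efficacy endpoints", without p-value adjustment. Missing data after rescue or discontinuation are handled in one of two ways: imputed as failure, or "the last observation prior to the rescue medication or subject discontinuation is carried forward to subsequent visits (LOCF").

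**The concern.** The other categorical secondary endpoints name something observed at the slit lamp or reported by the subject: no cells, no flare, Grade 0 pain. This one names a status and does not say, where it is listed, how a subject acquires it. A reader who collects every use of the term finds a rescue rule with a date, two rescue statements without a date, and a wider rule covering any discontinuation or missing value. The endpoint is also absent from a list whose wording presents it as complete.

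Two features of the analysis text add to the doubt. Testing at each visit does not suit an endpoint named for one visit. Carrying forward the last observation before rescue, if applied here, would turn a rescued subject back into a non-failure.

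At stake is whether two competent analysts would report the same failure proportions for a named efficacy endpoint that has its own test.

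**Working it through.** **The plan's own figures.** The documents give no rate, power or sample size for this endpoint. The nearest figures are those of Section 8.3 for the primary endpoints, at n = 196 per group and two-sided alpha 0.025 (z = 2.241):

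power = Φ{(d√n − z√(2p̄q̄)) / √(p₁q₁ + p₂q₂)}, where d = p₁ − p₂, p̄ is the mean of p₁ and p₂, and each q = 1 − p

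- AC cells, 0.283 v 0.143: (1.960 − 1.298)/0.570 = 1.16, so 87.7% (stated 87%).
- Pain, 0.739 v 0.486: (3.542 − 1.544)/0.665 = 3.00, so 99.9% (stated 99%).
- Simulating the two AC-cell tests with a shared vehicle group (250,000 trials) gives 96% for at least one difference and 80% for both (stated 95% and 80%).

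The coding of treatment failures enters none of these.

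**The text applied to each kind of subject.**

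| Subject | Governing text | Coding at Visit 5 |
|---|---|---|
| Rescue before Visit 5 | 6.2.3.1 | Failure |
| Rescue first received on the Visit 5 date | 6.2.3.1, which counts from the date of receipt | Failure |
| Rescue first received after Visit 5 | 6.2.3.1 | Not a failure at Visit 5 |
| Stopped before Visit 5 without rescue | 8.5.1.1, two approaches to missing data | Failure under the first approach |
| Missed Visit 5 but stayed in the study | No explicit rule; failure if handled as for the primary endpoints | Left open |

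The first three rows are settled by one sentence. Sections 6.3.1 and 6.3.2 add no date, but silence is not a conflict. The primary analysis counts rescue only if it came before the visit being summarized. That governs a different outcome and can stand beside Section 6.2.3.1.

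**LOCF.** Both approaches in Section 8.5.1.1 are for missing data. A rescued subject's failure status is not missing: before Visit 7, rescue is recorded on the Concomitant Medication eCRF and as the exit reason. Where the section assigns LOCF to particular outcomes, it names change from baseline, cells, flare and pain. It does not name treatment failures.

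**Testing at each visit.** An endpoint named for Visit 5 is tested at Visit 5. The general sentence cannot sensibly override the name.

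**Size of the part left open.** All rates here are assumed. The shift in the vehicle-minus-LE failure difference is (added vehicle − added LE)/196. With 1% to 5% of each group (2 to 10 subjects) stopping without rescue or missing Visit 5:

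- 10 vehicle, 2 LE: 8/196 = +4.1 points
- 2 vehicle, 10 LE: −8/196 = −4.1 points
- equal numbers: 0

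**Size if Section 6.2.3.1 were ignored for same-day rescue.** With 2% to 10% of vehicle (4 to 20) and 0% to 3% of LE (0 to 6) starting rescue on the Visit 5 date:

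- 20 vehicle, 0 LE: 20/196 = +10.2 points
- 4 vehicle, 6 LE: −2/196 = −1.0 point

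This range is wide because it pairs assumed extremes, and it concerns the case that Section 6.2.3.1 settles.

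**The case for a change.** The best argument for a change starts from the design. Visit 5 is itself a scheduled rescue assessment, so rescue starting on that date is to be expected. Section 8.5.1.1 says secondary endpoints use methods similar to the primary ones, and an analyst could import the primary rule that rescue must come before the visit. Nothing in Section 8.1.2 points to Section 6.2.3.1.

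The coding could also affect the test. Suppose rescue by Visit 5 is 10% on LE and 20% on vehicle. At unadjusted two-sided 0.05 with 196 per group, power is 79%. Adding 3%, 5% or 10% non-rescue loss to both groups lowers it to 73%, 70% or 63%. The repair would cost a few sentences and no new data.

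Part of this stands. No sentence links the endpoint to the rescue rule, one list is out of step, and the coding of a missed visit is not spelled out. The rest is weaker. The sentence about similar methods concerns tests; it does not redefine who has failed when another section says so by name. In the power illustration the difference stays at 10 points throughout, every rate is assumed, and the plan makes no power claim for this test.

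One could also read failure as non-response on a primary endpoint, which the planning rates would put at 85.7% v 71.7% for cells (1 − 0.143 and 1 − 0.283). That would only restate the complement of the primary result, and it relies on Section 8.5.9 outside its stated scope.

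**Conclusion.** No change to the plan is called for. The endpoint has a workable definition in Section 6.2.3.1: rescue received on or before the Visit 5 date. The apparent competing rule in Section 8.5.9 is limited to the primary endpoints. The omission from one synopsis list is clerical, since the body of the protocol and the synopsis endpoint list agree.

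The remaining gap is how to code discontinuation without rescue or a missed Visit 5. Analysts would sensibly fill it by imputing failure, as in the primary analysis and the first approach for secondary endpoints. The eCRF data on rescue and exit reason would let them show the rescue-only count beside it. Under an assumed 1% to 5% of each group in that gap, the difference moves by −4.1 to +4.1 points; the documents give no rates that would narrow this.

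The effect is confined to one unadjusted secondary comparison. The conclusion rests on reading the term as rescue-based, which three sections support. The study Statistical Analysis Plan to which the protocol refers may settle the coding further, but no such text is available here.
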